3.1 Design

Feasibility study to assess effectiveness of Microsoft HoloLens as an interactive communications tool in CTO PCI procedures.

3.2 Patients

Consecutive patients are included based on the following criteria:

3.2.1 Inclusion criteria

3.2.1.1 Clinical inclusion criteria

- Stable angina pectoris, or dyspnoea as an angina equivalent
- Age ≥ 18 yrs.
- Able to provide written informed consent

3.2.1.2 Angiographic inclusion criteria

- One or more completely occluded coronary arteries with Thrombolysis In Myocardial Infarction (TIMI) flow 0.
- An estimated occlusion duration of at least 3 months

3.2.1.3 Myocardial viability

- Absence of Q-wave in ECG leads corresponding to the occluded vessel, or documented viability of the main territory by MRI or echocardiography

3.2.1.4 Procedural inclusion criteria

- Clinical indication for CTO PCI regardless of operative technique

3.2.2 Exclusion criteria

- STEMI within 72 hours
- Cardiogenic shock
- Active bleeding or coagulopathy
- Life expectancy < 2 years
- Relevant allergies (aspirin, clopidogrel, ticagrelol, contrast compounds)
- Severe peripheral artery disease
- Clinical unstable angina

3.3 Study process

Study will be conducted by two participants where one is defined as expert or proctor and the other as operator who will perform the CTO procedure. Operator carries out the procedure in our institution while expert is located 300 km away. The plan is to conduct ten CTO procedures where the operator uses Hololens during the procedure and communicates with the proctor from the beginning to the end of procedure. Expert uses conventional laptop computer connected to Hololens to communicate and guide operator.

Guiding is performed by communication (sound) and Holographic interaction through Remote Assist software or similar Hololens applications. All participants are trained how to operate Hololens.

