2.2 Secondary objective

- a) To assess image quality, sound quality, multitasking, comfort, sterility, practicality, spatial awareness and possibility of communication with assisting nurse.
- b) Can use of HoloLens in CTO procedures increase effectiveness compared with conventional way of communication between operator and distanced proctor/co-operator
- c) Advantage of communication with HoloLens compared with traditional communication tools.
- d) To assess feasibility of using HoloLens in invasive cardiology procedures
- e) Does application of HoloLens technology cause limitations, including loss of spatial awareness, spatial disorientation, cabling, battery life and device discomfort.
- f) Does interaction between operator and proctor affect procedural endpoints like contrast volume, procedure time, fluoroscopy time, costs and procedural success

3. Methods

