3.4 Statistics

3.4.1 Statistical analyses will be performed in IBM SPSS for Windows (IBM Corp., Armonk, NY, USA). Values will be presented as mean \pm standard deviation, median (interquartile range) or no (%) as appropriate.

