4.2 Risks, side effects, advantages and disadvantages in participating in the study

Complex CTO PCI is in itself associated with decreased success rate and higher complication risk compared to ordinary PCI in non-occluded vessels. This study group finds no reason to believe there should be safety concerns connected to the use of Hololens guiding as by the described study protocol. The operator who will perform procedures is highly experienced with large volume of CTO procedures and treatment is based on proven treatment techniques. We are confident that interaction between operator and proctor during the CTO PCI may have differentiating potential in terms of procedural outcome due to complexity of CTO and great variation of techniques. In the case of disturbance or operators discomfort with device, the operator will simply remove device and continued procedure in the traditional fashion. We do not see ethical problems in using Hololens in CTO PCI procedures.

5. Patient information and informed consent

Patients will get written information about the study. Informed consent for participation in the study will be obtained from all patients. The patients will be informed that taking part is entirely voluntarily and that they can withdraw for study whenever they want. Withdrawal, or refusal to participate, will not influence treatment. Originals of signed consent forms will stay at the hospital and the patient will get a copy. It is the responsibility of investigators to ensure that informed consent has been acquired.

6. Biological material

Biological material will not be drawn or stored in the study

7. Enrolment period

Enrolment is expected to conclude in first quarter of 2022

8. Publication

Results will be published in a peer reviewed international cardiovascular journal.

9. Study group

A study group is responsible for this protocol, administrates the study implementation and progression.

17.10.2021

1. Fefer, P., et al. Current perspectives on coronary chronic total occlusions: the Canadian Multicenter Chronic Total Occlusions Registry. *J Am Coll Cardiol* 2012; 59: 991-7.
2. Brilakis, Emmanouil S., et al. "Guiding principles for chronic total occlusion percutaneous coronary intervention: a global expert consensus document." *Circulation* 140.5 (2019): 420-433.

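### Can procedures in which the HoloLens is taken off drop out of the ten, so that feasibility looks better than it was?

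*Protocol*

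**What the plan says.** Five places in the protocol bear on this.

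- Section 3.3 (Study process) describes the planned work as "ten CTO procedures where the operator uses Hololens during the procedure and communicates with the proctor from the beginning to the end of procedure". The number ten appears nowhere else as a target.
- Section 4.2 (Risks) provides for the device getting in the way: "In the case of disturbance or operators discomfort with device, the operator will simply remove device and continued procedure in the traditional fashion". It does not say how such a procedure is then counted.
- Section 3.2 (Patients) governs entry: "Consecutive patients are included based on the following criteria". The criteria that follow are clinical, angiographic, viability-related or procedural. All can be judged before the procedure starts, and none depends on how long the headset was worn.
- Section 2.2 (Secondary objective) includes, at d), "To assess feasibility of using HoloLens in invasive cardiology procedures" and, at e), "Does application of HoloLens technology cause limitations, including loss of spatial awareness, spatial disorientation, cabling, battery life and device discomfort".
- Section 3.4 (Statistics) is purely descriptive: "Values will be presented as mean \pm standard deviation, median (interquartile range) or no (%) as appropriate". No denominator is named for the percentages.

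**The concern.** Section 3.1 calls this a feasibility study, and section 4.2 gives discomfort with the device as one reason for removing it. Discomfort is also something that objective 2.2 e) sets out to assess. If the ten were only those procedures with the device and proctor in use throughout, a case would leave the denominator because of the very outcome under study.

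The share of procedures completed with the headset would then be 100% whatever happened. The ratings of comfort, image and sound under 2.2 a), and the procedural values under 2.2 f), would describe only cases in which the device was tolerated. With ten procedures, one or two lost cases are enough to change the message.

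**Working it through.** **Inputs.** The planned number, 10, is from section 3.3. The protocol gives no derivation for it (no precision target, power or expected rate), so there is no figure to reproduce. It also gives no removal rate, so the removal counts and probabilities below are assumptions.

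**Step 1: could removals occur at all?** With removal probability p per procedure, independent between procedures, the chance of at least one removal in ten is 1 − (1 − p)^10. The expected number of starts needed to reach ten full-use procedures is 10/(1 − p).

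| Assumed p | Chance of at least one removal in 10 | Expected starts for ten full-use cases |
|---|---|---|
| 5% | 1 − 0.95^10 = 40.1% | 10.5 |
| 10% | 1 − 0.90^10 = 65.1% | 11.1 |
| 20% | 1 − 0.80^10 = 89.3% | 12.5 |
| 30% | 1 − 0.70^10 = 97.2% | 14.3 |

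So the question is not idle.

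**Step 2: what would the counting rule do?** The intervals are exact (Clopper-Pearson) 95% limits for x completions in n. The lower limit is the 0.025 quantile of Beta(x, n − x + 1), and the upper limit is the 0.975 quantile of Beta(x + 1, n − x). When x = n the lower limit is 0.025^(1/n) and the upper limit is 100%.

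| Assumed removals | First ten started, all counted | Removals dropped | Removals replaced: reported | Removals replaced: share of all started |
|---|---|---|---|---|
| 1 | 9/10 = 90% (55.5 to 99.7) | 9/9 = 100% (66.4 to 100) | 10/10 = 100% (69.2 to 100) | 10/11 = 90.9% (58.7 to 99.8) |
| 2 | 8/10 = 80% (44.4 to 97.5) | 8/8 = 100% (63.1 to 100) | 10/10 = 100% (69.2 to 100) | 10/12 = 83.3% (51.6 to 97.9) |
| 3 | 7/10 = 70% (34.8 to 93.3) | 7/7 = 100% (59.0 to 100) | 10/10 = 100% (69.2 to 100) | 10/13 = 76.9% (46.2 to 95.0) |

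Each removal moves the figure by 1/10, or 10 percentage points, if counted, and by nothing if dropped or replaced.

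**Step 3: does the protocol adopt a dropping or replacing rule?** The distortion in Step 2 needs such a rule, so the text decides the matter.

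- Section 3.3 states what is planned to happen. It sits under the study process and is not worded as a condition for being evaluable or analysed.
- Section 4.2 says what happens if the plan cannot be followed. An intended intervention with freedom to stop it is the usual arrangement in a trial, and stopping does not by itself take the patient out. The section mentions no exclusion, withdrawal or replacement.
- Section 3.2 fixes who is in the study, by consecutive entry on baseline criteria. A patient who met them and consented still meets them after the headset comes off.
- Objectives 2.2 d) and e) can be answered only if removals are reported.
- Neither section 2.1 nor section 2.2 names completion with the device as an endpoint. The percentages in Step 2 illustrate a statistic that the protocol does not promise.

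Taken together, the sections point to counting every started procedure, the first column of results in the Step 2 table.

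**The case for a change.** The best case for acting is that section 3.3 is the only text that specifies the ten, so an investigator counting towards ten has no other rule to apply. Section 3.2 says who enters. It does not say when the tenth procedure has been reached or what the percentages in section 3.4 are divided by, so a patient could be enrolled and still not be thought of as one of the ten. Replacement would also be decided as procedures take place, and a later SAP could not recover ratings that nobody collected after a removal. The cost of preventing this is small: a sentence or two and a line on the case form.

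Part of this stands. The protocol nowhere says how a procedure with a removal is counted, and one sentence would settle it at no cost to the operator's freedom to remove the device. But the argument shows only that a poor rule is possible. It does not show that the protocol contains one. Nothing provides for replacement, nothing makes the ratings conditional on full use, and the objectives pull the other way. An analysis set and the handling of a discontinued intervention are ordinary SAP content. The SAP is not at hand, so their absence from the protocol is not an error.

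**Conclusion.** No change to the plan is called for. Sections 3.3 and 4.2 stand to each other as intention and contingency, so they do not conflict. The plain reading of section 3.2 keeps a procedure with a removal among the ten.

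If someone did drop or replace such cases, the effect would be material: 100% reported instead of 90%, 80% or 70% for one, two or three assumed removals in ten. That result depends on a counting rule which the protocol does not state, on removal counts which it does not give, and on a completion rate which it does not list as an endpoint.

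What remains is a detail that an analyst would fill sensibly: count every procedure started with the headset and report removals with time and reason. Writing this down would be a harmless clarification, but the plan is not wrong without it. This conclusion would change only if the SAP or the case form, neither of which is shown, restricted the ten to procedures with full device use or replaced the others.

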2.1 Primary objective

Assess Microsoft HoloLens as an interactive communication device in remote proctoring, and enhancement of teamwork in complex CTO procedures.

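### Do the wide wording of objective 2.2 d and the open choice of HoloLens software call for a change in a ten-case CTO study?

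*Protocol*

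**What the plan says.** Section 2.2 lists as secondary objective d: "To assess feasibility of using HoloLens in invasive cardiology procedures". The sections around it are narrower. The primary objective in 2.1 concerns HoloLens in remote proctoring and "enhancement of teamwork in complex CTO procedures". Section 3.1 describes the design as a "Feasibility study to assess effectiveness of Microsoft HoloLens as an interactive communications tool in CTO PCI procedures". The procedural inclusion criterion in 3.2.1.4 is a clinical indication for CTO PCI.

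Section 3.3 states that two people conduct the study, one as proctor and one as operator, and gives the number of cases: "The plan is to conduct ten CTO procedures where the operator uses Hololens during the procedure". The proctor works from a laptop and guides the operator by sound and by "Holographic interaction through Remote Assist software or similar Hololens applications". On preparation, the same section says: "All participants are trained how to operate Hololens". Section 4.2 adds: "The operator who will perform procedures is highly experienced with large volume of CTO procedures".

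Section 3.4 is purely descriptive: mean and standard deviation, "median (interquartile range) or no (%) as appropriate". It plans no test, no subgroup and no split by software. Section 3.5 covers coding and storage of data and lists no data fields of any kind.

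**The concern.** Two separate things attract attention.

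The first is scope. Objective 2.2 d names a whole field, while the data can come from only one type of procedure, one operator and one proctor. Sections 1.1 and 4.2 themselves set CTO PCI apart from PCI of non-occluded vessels, with lower success and more complications. A good result in ten such cases could be reported as feasibility in invasive cardiology at large.

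The second is the intervention. Section 3.3 names one application and then admits similar ones. Objective 2.2 a asks about image quality, sound quality and practicality, which the software may well affect. If the application changed part-way, a single pooled figure would describe neither system, and a summary in the formats of 3.4 would not reveal the change. A split by application would then be possible only if the application had been noted for each case.

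**Working it through.** **No stated figure to reproduce.** The protocol gives ten procedures as a plain count, with no alpha, power, effect size or precision target. The check is therefore a comparison of passages, followed by illustrations whose extra inputs are assumptions.

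**Scope.**

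| Place in protocol | Scope |
|---|---|
| 2.1 | CTO procedures |
| 2.2 d | Invasive cardiology procedures |
| 3.1 | CTO PCI |
| 3.2.1.2 and 3.2.1.4 | Occluded vessel, indication for CTO PCI |
| 3.3 | Ten CTO procedures, one operator, one proctor |

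Only 2.2 d is wider. It contains the others and does not contradict them, since CTO PCI is one kind of invasive cardiology procedure. Section 1.5 says that, to the authors' knowledge, the device had not been used in clinical practice in interventional cardiology. Objective 2.2 d therefore reads naturally as a question of first use in that field. No eligibility rule, data item or summary depends on its wording.

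**Software.** Section 3.3 permits an alternative application. It does not say that the application will change between cases, and its wording fits equally well with choosing one product before the first case. The headset is common to all cases.

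**What a switch could do (splits and shifts assumed).** Suppose *n* = 10 and two applications differ by 1 within-application SD.

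- Switch after case 7: the pooled mean lies 3/10 = 0.3 SD from the first application's mean and 7/10 = 0.7 SD from the second's.
- Sum of squares of the case means about the pooled mean: SS = 7 × 3/10 = 2.1. Pooled SD factor: √(1 + SS/(n − 1)) = √(1 + 2.1/9) = 1.111, a rise of 11%.
- Switch after case 5: SS = 5 × 5/10 = 2.5. Factor: √(1 + 2.5/9) = 1.130, a rise of 13%.
- Chance range of a sample SD at n = 10, from √(χ²₉/9): 0.548 to 1.454 times the true value (95%). Both rises lie well inside it.

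A pooled SD would therefore not show a switch of this size. That is no fault in section 3.4, because nobody uses the SD for that purpose.

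**Precision for a yes/no outcome (assumed; the protocol defines none).** With success in every case, the exact two-sided 95% lower limit is 0.025^(1/n).

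| Cases, all successful | Lower limit |
|---|---|
| 10 | 69.2% |
| 7 | 59.0% |
| 5 | 47.8% |
| 3 | 29.2% |

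The 69.2% limit follows from the choice of ten cases and holds whatever 2.2 d says and whichever software is used. The other rows show that a split by application would leave each part with very little information, so a planned split would gain little.

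**The case for a change.** The strongest case for a change is that objectives and the definition of the intervention belong in the protocol. A SAP can add tables, but it cannot split results by an application that nobody wrote down. The remedy would be cheap: reword one objective, name one application, and note the application and version for each case. It would have to be settled before the procedures begin.

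Part of this stands. Objective 2.2 d is worded more broadly than the study, and section 3.3 does leave the software open. A tidier protocol would limit the first to CTO PCI and name the second.

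The rest does not carry. Sections 3.3 to 3.5 list no data fields at all, so the absence of one for the application is not evidence that it would go unrecorded. Such fields usually sit in a case report form, and case listings or exact intervals in a SAP; neither was available here. With ten cases and one operator, a change of software would be obvious to the people running the study, and an analyst would report it. Naming one application with a fallback in case of failure would still permit a switch, so pooled summaries could still mix systems. That results come from a single experienced operator and one proctor is stated openly in sections 3.3 and 4.2, and belongs among the limitations when results are reported.

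**Conclusion.** No change to the plan is needed. The wording of 2.2 d is loose, but it creates no contradiction, and narrowing it would alter neither the data collected nor any summary. The open choice of application is a gap that sensible study conduct fills. Followed as written, the plan gives sound descriptive results for ten CTO PCI procedures.

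The size of any effect cannot be taken from the protocol. The 11% and 13% rises in the pooled SD rest on an assumed switch and an assumed shift of 1 SD, and the lower limits for 7, 5 and 3 cases rest on an assumed split and an assumed yes/no outcome. No figure that the protocol states is wrong. The conclusion assumes that the application is chosen before the start or, if it has to change, that the change is noted and reported. It would be different if the study intended to use several applications and pool them without saying so, and nothing in the protocol suggests that.

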3.4 Statistics

3.4.1 Statistical analyses will be performed in IBM SPSS for Windows (IBM Corp., Armonk, NY, USA). Values will be presented as mean \pm standard deviation, median (interquartile range) or no (%) as appropriate.

3.5 Data management

Each participant will be given a unique study subject number. A list of participating patients and their respective study numbers will be kept in a secure place in a locked office. Patient data will be stored in a de-identified manner in a secure database.

4. Ethical aspects

4.1 This study is conducted in accordance with the protocol, applicable regulatory requirements and the declaration of Helsinki. The primary investigator has the responsibility to obtain approval of the study protocol, the patient information and the informed consent.

4.2 Risks, side effects, advantages and disadvantages in participating in the study

Complex CTO PCI is in itself associated with decreased success rate and higher complication risk compared to ordinary PCI in non-occluded vessels. This study group finds no reason to believe there should be safety concerns connected to the use of Hololens guiding as by the described study protocol. The operator who will perform procedures is highly experienced with large volume of CTO procedures and treatment is based on proven treatment techniques. We are confident that interaction between operator and proctor during the CTO PCI may have differentiating potential in terms of procedural outcome due to complexity of CTO and great variation of techniques. In the case of disturbance or operators discomfort with device, the operator will simply remove device and continued procedure in the traditional fashion. We do not see ethical problems in using Hololens in CTO PCI procedures.

5. Patient information and informed consent

Patients will get written information about the study. Informed consent for participation in the study will be obtained from all patients. The patients will be informed that taking part is entirely voluntarily and that they can withdraw for study whenever they want. Withdrawal, or refusal to participate, will not influence treatment. Originals of signed consent forms will stay at the hospital and the patient will get a copy. It is the responsibility of investigators to ensure that informed consent has been acquired.

6. Biological material

Biological material will not be drawn or stored in the study

7. Enrolment period

Enrolment is expected to conclude in first quarter of 2022

8. Publication

Results will be published in a peer reviewed international cardiovascular journal.

9. Study group

A study group is responsible for this protocol, administrates the study implementation and progression.

17.10.2021

1. Fefer, P., et al. Current perspectives on coronary chronic total occlusions: the Canadian Multicenter Chronic Total Occlusions Registry. *J Am Coll Cardiol* 2012; 59: 991-7.
2. Brilakis, Emmanouil S., et al. "Guiding principles for chronic total occlusion percutaneous coronary intervention: a global expert consensus document." *Circulation* 140.5 (2019): 420-433.
